Patients will be identified as potential subjects in Neurosurgery or Pain clinic. The potential subject will then be approached by a member of the research team to discuss the study. After the study is thoroughly explained and all questions are answered, the subject will be asked to sign a formal written consent.

Patients will be drawn from the general pool of patients undergoing spinal cord stimulation for chronic pain. Of this pool for already implanted patients, those patients who additionally have restless leg syndrome (RLS) will serve as the experimental population, while those patients who do not meet criteria for RLS will serve as the control population.

IX. Inclusion Criteria

- All subjects will be between the ages of 18-85.
- All subjects will have the mental capacity to understand and decide to participate in the research.
- All subjects will recently have undergone or are planning to undergo SCS implantation (thoracolumbar region) for chronic pain, as defined by standard clinical criteria used by the UIHC Pain Clinic for neuromodulation therapy (having failed conservative measures, surgery, and other interventional pain procedures).

Group 1 and 2 will be divided based on if they have Restless Leg Syndrome (n=25) or do not have Restless Leg Syndrome (n=25, control group).

X. Exclusion Criteria

- <18 or >85 years of age
- Non-English speakers

XI. Study Procedures

For RLS subjects will be instructed to discontinue their RLS medications 48 hours prior to visits #1 & #2.

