For Visit 1: The subject will arrive to the CRU for their appointment which will take 4 hours. The subject will have been fasting for 8 hours, refrain from moderate or vigorous exercise for at least 24 hours, refrain from drinking alcohol for at least 24 hours prior to the visit. Any female subjects will undergo a urine pregnancy test prior to the study beginning. If the pregnancy test is positive, the subject will no longer be eligible to continue with the study. DEXA scan will be done. Subject will be asked to wear comfortable clothes that doesn't contain any metal or reflective surfaces as this may skew the results. Subjects will lay on the table. The procedure will take 10-15 minutes. An IV catheter will be placed in the subject's arm by a RN, after 20 minutes the nurse will draw blood from the IV catheter to measure sugar, insulin, cholesterol, and catecholamine. A blood pressure cuff will be placed around the subject's upper arm and blood pressure will be recorded 2-3 times. 3 EKG stickers will be placed on the subject's chest so that heart rate and rhythm can be monitored. A non-invasive tonometer probe will be placed on the subject's wrist, arm, neck, upper/inner thigh, and ankle to record the pulse at these sites. The blood flow to the subject's arm or leg may also be measured by placing a probe on the skin over the femoral artery of the leg or the brachial artery of the arm. Transcutaneous recordings will be captured to measure oxygen and carbon dioxide by placing monitors on the subject's chest and foot. Calf blood flow using venous occlusion plethysmography (VOP): VOP will be used to measure calf blood flow (CBF) responses to local ischemia to test endothelium-dependent dilation of calf resistance arteries. Briefly, subjects lie supine and have blood pressure cuffs (venous occlusion) placed around upper thigh and pediatric blood pressure cuffs around ankle. CBF will be measured by placing a gallium-in-silastic strain gauge around the widest part of the calf which measures small changes in calf volume during periodic inflation (8 sec inflated:4 sec deflated) of upper thigh cuffs to 40 mmHg (which temporarily prevents venous outflow and measures arterial inflow into calf) and continuous ankle inflation of a blood pressure cuff to 250 mmHg. VOP is a well-established and validated technique for measuring limb response to ischemia in human subjects and is expressed in ml/100 ml tissue/min. Calf vascular conductance, to determine blood flow adjusted for mean arterial pressure, will be calculated as blood flow/mean arterial pressure, expressed as ml/min/100mmHg. If the subject is taking any morning medications, the research team may ask the subject to not take them in the morning but bring them with to the study and take at the end of the visit. At the end of visit 1, the participant will be sent home with a 24-hour ambulatory blood pressure monitor (AMBP) that will be worn for 2 days; one with the stimulator on and one with the stimulator off.

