Ambulatory blood pressure cuff visit: A visit for the placement of a Continuous ambulatory blood pressure cuff may be added for any willing participants. A subset of participants will only be completing the Continuous ambulatory blood pressure cuff study and will sign a separate consent form. Participants will complete a diary (data collection sheet) while wearing the blood pressure cuff that will include time of activities, sleep, and time of SCS activation and deactivation. Participants will be given a shipping box with postage to return the blood pressure cuff and diary if unable to physically return to the Clinical Research Unit. The time of this visit will take place at the convenience of the participant. While wearing the Continuous ambulatory blood pressure cuff, participants will refrain from any RLS medications (48hours).

Enrolled subjects are eligible to come back for a third unscheduled visit to complete study related interventions that were not completed during the scheduled two visits if they wish.

XII. Possible Risks of the Study

Emotional or psychological: There are no foreseeable emotional or psychological risks with this study. But there is risk of inadvertent disclosure of PHI which could cause emotional or psychological risk.

Physical: The nerve recording procedure (microneurography) occasionally may result in the leg muscles feeling tired. Also, the patient may have a pins-and-needles feeling or a greater sensitivity to touch in the leg. However, these side effects rarely occur and do not usually last more than a couple of minutes. The ambulatory blood pressure monitor may cause some discomfort and could potentially bruise or scratch the participant's arm, though this is not very common.

The potential risk and discomfort from the blood draw may result in any of the following to occur slight bruising, pain, a temporary feeling of faintness, and rarely an infection at the site of the blood draw.

The pulse wave velocity has no known risks associated with the use of the non-invasive pulse transducer, but the ECG electrodes that are used may cause minor irritation to the skin

Fasting for 8 hours prior to participating in the study may cause dehydration. You will be encouraged to drink plenty of water, subjects may experience hunger and irritability. if the subject would experience nausea, vomiting, or fainting the subject will be instructed to stop fasting.

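### The two routes to ambulatory blood pressure carry different RLS-drug rules and the on/off day order is not set, so Hypothesis 3 is open to bias from drug washout

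*Protocol*

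**What the plan says.** Three places in Protocol section XI (Study Procedures) bear on RLS drugs during ambulatory BP recording.

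- **Opening sentence.** RLS subjects are to "discontinue their RLS medications 48 hours prior to visits #1 & #2". Nothing is said about what follows the visit.
- **Visit 1 paragraph.** The visit takes 4 hours. "At the end of visit 1, the participant will be sent home with a 24-hour ambulatory blood pressure monitor", to be "worn for 2 days; one with the stimulator on and one with the stimulator off". No RLS-drug rule covers those two days. Subjects asked to hold back morning medications may "bring them with to the study and take at the end of the visit"; RLS drugs are neither named nor excluded there.
- **Ambulatory blood pressure cuff visit paragraph.** While wearing the cuff, "participants will refrain from any RLS medications (48hours". No stop before placement is given. The visit is open to any willing participant, and "A subset of participants will only be completing the Continuous ambulatory blood pressure cuff study". A diary records when stimulation is switched on and off, but not when drugs were last taken.

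Hypothesis 3 (Protocol section VI) is that stimulation lowers 24-hour BP more in patients with RLS than in those without. Neither document fixes, randomises or balances the order of the on day and the off day. The SAP names a model only for femoral and brachial blood flow. It has no ambulatory BP analysis and no term for day order, route or drug state.

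**The concern.** Hypothesis 3 is a difference between groups in a within-person contrast: BP with the stimulator on minus BP with it off, on two different days. Anything that shifts BP between day 1 and day 2 in one group more than in the other can pass for a difference in stimulation effect unless day order is balanced. Drug washout is a candidate. The section XI opening sentence directs only RLS subjects to stop drugs, and the protocol's own Background credits the main drug class for RLS with a peripheral vasodilator action.

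The routes matter because they can place the recording at different points of the washout. A recording that begins at the last dose spans the steepest part; one that begins two days later spans the tail.

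There is also a reporting gap. Section XII (Possible Risks) does not mention withholding RLS drugs, and the total time off drug cannot be worked out from section XI as written.

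**Working it through.** **Inputs.** From Protocol section XI: stop 48 h before Visit 1; visit length 4 h; wear 2 days; 48 hours in the cuff-visit sentence. From section IX: 25 patients per group. The BP drift and the drug half-lives below are assumptions; the documents give neither.

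**1. The plan's own 48 hours.** 2 days × 24 h = 48 h, so the figure matches the wear period. It also equals the stop before Visits 1 and 2, so the number alone does not settle which is meant.

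**2. Time since last RLS dose when recording starts.**

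- Visit 1 route, drugs not resumed: at least 48 + 4 = 52 h.
- Visit 1 route, drugs resumed at the end of the visit: recording is made on drug.
- Cuff route, 48 hours read as the wear period: as little as 0 h.
- Cuff route, 48 hours read as a stop before placement: 48 h or more.

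With drugs not resumed after Visit 1, the routes differ by up to 52 h on the first cuff reading and by about 52 − 48 = 4 h on the second.

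**3. How a drift enters Hypothesis 3.** Let τ be the true on-minus-off effect and d the mean change in BP from day 1 to day 2 in the RLS group that is due to washout.

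- On first: on − off = τ − d
- Off first: on − off = τ + d
- With share p on first, the mean is τ + d(1 − p) − dp = τ + d(1 − 2p)

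If controls have no such drift, the group comparison carries the same bias, d × (1 − 2p). For assumed d, in mmHg:

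| d | p = 0 | p = 0.25 | p = 0.5 | p = 0.75 | p = 1 |
|---|---|---|---|---|---|
| 1 | 1 | 0.5 | 0 | −0.5 | −1 |
| 3 | 3 | 1.5 | 0 | −1.5 | −3 |
| 5 | 5 | 2.5 | 0 | −2.5 | −5 |

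A negative bias looks like a larger BP fall with stimulation. If washout raises BP, an on-first order therefore favours Hypothesis 3. That direction is an inference, not a document statement.

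**4. Which start time drifts most.** Assume first-order elimination with half-life h and k = ln 2 / h. The mean residual fraction between a and b hours is (e^(−ka) − e^(−kb)) / (k(b − a)). For h = 12 and a start at 0 h, day 1 gives 0.541 and day 2 gives 0.135, a fall of 0.406. Fall from day 1 to day 2:

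| Half-life | Start 0 h | Start 48 h | Start 52 h |
|---|---|---|---|
| 6 h | 0.317 | 0.001 | 0.001 |
| 12 h | 0.406 | 0.025 | 0.020 |
| 24 h | 0.361 | 0.090 | 0.080 |

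The drift comes mainly from a start at 0 h, that is, from the cuff route read as withholding during wear only.

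**5. What balancing achieves.** The nearest split of 25 is 13 to 12. The bias is then d × (1 − 2 × 13/25) = −0.04d, or 4% of the drift.

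**The case against.** The strongest reply is that none of this shows Hypothesis 3 to be confounded. A drug state that is constant over both days and adds to BP cancels within the person. Route is open to both groups, so a route difference alone gives heterogeneity among RLS patients, not a group difference. Bias needs both a drift and an unbalanced order; the order is unstated, not known to be unbalanced, and the cuff-visit diary lets the actual order be checked afterwards. All of that stands.

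A reader might also infer more from the hours than they support:

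- **A stated 0 h start by the cuff route.** It is the minimum under one of two readings.
- **100 hours off drug by the Visit 1 route (48 + 4 + 48).** This needs withholding to continue through the wear period, which the Visit 1 paragraph does not say. Its sentence on morning medications leaves resumption open.
- **A drift confined to the RLS group.** This is a fair inference from the opening sentence of section XI, but the cuff-visit sentence addresses all participants and RLS medications are not defined. A control with chronic pain might take a drug that counts.
- **A definite bias in mmHg.** Neither the drift nor the share using each route is given, and the lower bound is zero.

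The reply does not remove the gap. If drugs are resumed after Visit 1, the two routes record under opposite drug rules. A diary can reveal an unbalanced order but cannot repair it: if everyone has the same order, day and stimulation cannot be separated.

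**Conclusion.** The point holds in conditional form. The drug rules in section XI differ by route and leave the drug state during recording undetermined: at least 52 h off drug, or drugs resumed, by the Visit 1 route; from 0 h, or from 48 h or more, by the cuff route. With no day order set and no ambulatory BP analysis in the SAP, Hypothesis 3 is open to a bias of d × (1 − 2p), from zero with balanced order up to the full drift with a single common order. This assumes that washout moves 24-hour BP and does so mainly in RLS patients; the size of d is unknown.

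It should be fixed because the remedy is cheap, not because bias has been shown. One limit remains even with balanced order: if withdrawal changes the response to stimulation itself, the group comparison cannot separate RLS status from the drug-withdrawn state.

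**What to change.** 1. **Reconcile the three places in section XI** into one RLS-drug statement covering both routes and the whole wear period, and say to whom it applies. The clinical content is for the sponsor. State the resulting total time off drug in section XII.
2. **Randomise the order of the on and off days within each group**, in blocks, stratified by route if numbers allow. This makes the expected bias from drift zero.
3. **Add the time of the last RLS dose to the diary**, and use the diary for wear after Visit 1 as well.
4. **Write the Hypothesis 3 analysis into the SAP**: group by stimulation, with period and group-by-period terms, and a sensitivity analysis by route. A common period term would not remove a drift specific to RLS patients, and a route main effect lies between subjects and leaves the on/off contrast unchanged. The group-by-period term can be estimated only if day order varies within group, so step 2 must come first.

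Cost: protocol wording, a day-order list, one diary field and a little more analysis. No added visits or measurements.

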
For visit 2: The subject will arrive to the CRU for their appointment which will take 4 hours. The subject will have been fasting for 8 hours, refrain from moderate or vigorous exercise for at least 24 hours, refrain from drinking alcohol for at least 24 hours prior to the visit. Any female subjects will undergo a urine pregnancy test prior to the study beginning. If the pregnancy test is positive, the subject will no longer be eligible to continue with the study. An IV catheter will be placed in the subject's arm by a RN, after 20 minutes the nurse will draw blood from the IV catheter to measure sugar, insulin, cholesterol, and catecholamine. A non-invasive tonometer probe on will be placed on the subject's wrist, arm, neck, upper/inner thigh, and ankle to record the pulse at these sites. The blood flow to the arm or leg may also be measured by placing a probe on the skin over the femoral artery of the leg or the brachial artery of the arm. Transcutaneous recordings will be captured to measure oxygen and carbon dioxide by placing monitors on the subject's chest and foot. The subject's heart rate will be measured by using an ECG and the subject's blood pressure will be monitored indirectly with an automatic cuff device on one of the subject's fingers. The sympathetic nervous system activity to the subject's leg muscles will be measured by a tiny microelectrode placed in a nerve in the right leg located just below the knee on the outer part of the leg. When the nerve is stimulated, an involuntary twitching or tingling sensation of the lower leg or foot will occur. The sensation will disappear when the stimulation is stopped. When the nerve is located 2 tiny sterile microelectrodes will be inserted through the skin. VOP (venous occlusion plethysmography) testing to measure calf blood flow. If the subject is taking any morning medications, the research team may ask the subject to not take them in the morning but bring them with to the study and take at the end of the visit. If DEXA scan hasn't been completed during visit 1, it will be completed during visit 2. Subject will be asked to wear comfortable clothes that doesn't contain any metal or reflective surfaces as this may skew the results. Subjects will lay on the table. The procedure will take 10-15 minutes.

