 - 6) Important medical events that may not result in death, be life-threatening, or require hospitalization may be considered a serious adverse drug event when, based upon appropriate medical judgment, they may jeopardize the patient or subject and may require medical or surgical intervention to prevent one of the outcomes listed above.
- Receipt of new information

During the course of a study, researchers may become aware of new information that would impact a subject's decision to participate or continue participating in the research study. For example, interim analyses of data may identify a trend which impacts the safety of subjects or may identify early efficacy (benefit) of one of the interventions under study. In addition, results from other research studies or changes in standards of practice or care may affect conduct of a study and would need to be communicated to research subjects.
- Noncompliance

Noncompliance is a failure to follow the federal regulations with respect to protection of human subjects in research or failure to follow the determinations of the IRB with respect to conduct of the research as approved by the IRB.

Once per year, the IRB is required to review and approve all non-exempt research projects at intervals appropriate to the degree of risk, but not less than once a year. This is called "continuing review." Continuing review for non-exempt research is required to occur as long as the research remains active for long-term follow-up of the research subject, even when the research is permanently closed to the enrollment of new subjects and all subjects have completed all research-related interventions and to occur when the remaining research activities are limited to collection of private identifiable information.

Adverse Event Collection:

The clinical research team is responsible for collecting and recording the research data. As the results are collected, all adverse events will be identified after an informed consent is signed by the subject or their legally authorized representative (LAR) and the medication is initiated.

Throughout the study, during all follow-up visits, in addition to the medical chart review, adverse events are to be elicited by the investigator (or designate) by asking the subject non-leading questions. All AEs and SAEs will be reported to the principal investigator (PI) and the PI will determine the final relationship of the event to the investigational product.

XIV. Data Management

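### Adverse-event questioning is tied to follow-up visits, but no contact is scheduled after the Visit 2 nerve recording or a posted-back cuff, so no one is certain to be asked about late effects

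*Protocol*

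**What the plan says.** Section XIII of the protocol (Adverse Event Collection) reads: "Throughout the study, during all follow-up visits, in addition to the medical chart review, adverse events are to be elicited". The questions are to be non-leading and put by the investigator or a delegate. The sentence before it starts identification of events after consent "and the medication is initiated". The section does not say what a follow-up visit is, when charts are reviewed, or when collection ends.

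Section XI describes the contacts. Visits 1 and 2 are each introduced with "The subject will arrive to the CRU for their appointment which will take 4 hours". The nerve recording appears only under Visit 2: "When the nerve is located 2 tiny sterile microelectrodes will be inserted through the skin". Beyond these, "Enrolled subjects are eligible to come back for a third unscheduled visit to complete study related interventions"; this is at the participant's choice and covers whatever the two planned visits left undone. A cuff visit may also be added at a time that suits the participant, and some people take part in the cuff study alone. For those who cannot come back in person, "Participants will be given a shipping box with postage to return the blood pressure cuff and diary". The diary is to record activities, sleep and stimulator on/off times.

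Section XII names tired leg muscles, pins-and-needles and increased sensitivity to touch as possible effects of the nerve recording, and adds that "these side effects rarely occur and do not usually last more than a couple of minutes". Section XV says the study team can be reached at any hour. The SAP contains no adverse-event analysis.

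**The concern.** The rule for asking about harms is attached to a type of visit that the schedule does not contain. The recording that puts electrodes into a leg nerve is done at the last scheduled visit, so no later planned occasion exists to ask whether a symptom persisted or appeared after the participant went home. The posted-cuff route has the same gap: the participant is at home, switching the stimulator and (if they have RLS) off RLS medication, and the listed diary content has no place for harms.

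Two things are at stake. First, Section XII says the effects do not usually last, which allows that some might. Those are the effects for which the plan guarantees no question. Second, the protocol describes RLS itself as a disturbing sensation in the legs, and the named effects of the recording are also leg sensations. No question about leg symptoms before electrode insertion is described, so an investigator judging relatedness would have no described baseline.

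**Working it through.** The plan states no adverse-event rate, so there is no figure to reproduce. The check sets the schedule against the questioning rule and then works out what a zero count could support.

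**Step 1. Contacts after each exposure (Protocol Section XI).**

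| Exposure | Scheduled contacts afterwards | Optional contacts afterwards |
|---|---|---|
| Cuff worn for 2 days after Visit 1 | 1 (Visit 2) | third visit, added cuff visit |
| Nerve recording at Visit 2 | 0 | third visit, added cuff visit |
| Posted-back cuff, cuff-only participant | 0 | none described |
| Posted-back cuff, cuff visit added after Visit 2 | 0 | third visit |

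The gap therefore covers the Visit 2 recording and two kinds of posted cuff. It does not cover the cuff worn between Visits 1 and 2.

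**Step 2. What remains for late effects.** Three sources are left: chart review (Section XIII), which finds events that reached care; participant-initiated contact (Section XV), which finds events that are volunteered; and the optional visits, which occur only for some people. None yields a number of participants asked.

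**Step 3. Start of collection.** Section XIII requires both consent and the start of a medication. Section XI gives no study medication, and the stimulators are implanted for chronic pain. The second condition has nothing to refer to, so the start of the window is undefined as well as its end.

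**Step 4. What zero events would support.** With *n* people asked and none reporting a persisting symptom, the exact one-sided 95% upper limit *p* solves (1 − p)^n = 0.05, so p = 1 − 0.05^(1/n).

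- n = 50 (planned total): p = 1 − 0.05^(1/50) = 1 − 0.9418 = 0.058, or 5.8%.
- n = 25 (one group, or half the total): p = 1 − 0.05^(1/25) = 1 − 0.8871 = 0.113, or 11.3%.

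Both values of *n* are assumptions. The documents do not say how many participants will have the recording, how large the cuff-only subset is, or whether it counts within the 50. A smaller *n* gives a wider limit. If no one is asked, *n* is unknown and the formula cannot be used.

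**The case against.** The strongest reply is that the plan does more than this suggests, and much of it stands.

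- A reader might infer that events are collected only at follow-up visits. The documents do not support that: the same sentence speaks of the whole study and adds chart review, and Section XV offers contact at any hour.
- A reader might infer that late effects can never be asked about. That also goes too far. A third visit or an added cuff visit could follow Visit 2 and would be an occasion to ask. Such an occasion is possible but not guaranteed.
- A reader might infer that only the minutes before departure are observed. Visit 2 lasts 4 hours, and the effects Section XII expects would mostly fall within it. Whether Visit 2 counts as a follow-up visit is unclear, but the gap concerns late or persisting effects.
- A reader might infer that no baseline exists. The documents show only that none is described: case report forms are mentioned but not supplied, and Section XV refers to screening for risk factors.
- The protocol does not rank its procedures by risk, so calling the nerve recording the riskiest would be a reviewer's judgement.
- The study is mechanistic. No aim in Section VI and no analysis in the SAP sets out to estimate a complication rate.

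The last point limits the importance of the gap but does not close it. Section XIII itself commits to active questioning, and after Visit 2 that commitment has no scheduled occasion. Chart review and volunteered reports can reveal a persisting effect, but their silence cannot be read as its absence.

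**Conclusion.** The concern holds for late and persisting effects. Scheduled contacts after the nerve recording: 0. Scheduled contacts after a posted-back cuff, for cuff-only participants or a cuff visit added after Visit 2: 0. Such effects rest on chart review, volunteered reports and optional visits, without a denominator.

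In size, this is the difference between being able to state an upper limit of 5.8% (50 asked, none affected) or 11.3% (25 asked, none affected) and being able to state none. Those limits assume that everyone counted had the recording and was asked. The gap does not touch the physiological comparisons. It is a modest weakness in safety capture that is worth correcting because the correction is cheap.

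**What to change.** In Section XIII, replace the reference to follow-up visits with named contacts:

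1. Non-leading adverse-event questions at every visit. At Visit 2, ask about existing leg paraesthesia before electrode insertion and again before the participant leaves.
2. One scripted telephone call at a fixed interval after Visit 2, with follow-up of any new leg symptom. About 7 days is a suggestion; the documents give no figure.
3. An adverse-event line in the cuff diary, and a brief call when a cuff comes back by post.

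Start collection at consent, and delete the condition about a medication. Report persisting leg symptoms with the number of participants contacted as the denominator.

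The cost is a protocol amendment, a short call script, and small additions to the case report form and diary. Existing staff would make about one short call per participant (at most 50 if all 50 have the recording), plus cuff-return calls and occasional repeat calls. No invasive procedure is added, and endpoints and eligibility are unchanged.
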